## **Eligibility criteria**

### **Inclusion criteria**

- Adults ( $\geq 18$  years)
- Presentation compatible with hyperacute stroke syndrome
- One or more of the following symptoms present at time of enrolment: Dysphasia, neglect (NIHSS 1-2), hemianopia (NIHSS 1-3), or limb weakness (NIHSS on affected arm and/or leg 1-4)
- Treatment can be commenced between 3 and 5 hours from onset of symptoms (for patients with wake-up stroke, treatment no more than 5 hours after patient awakens)
- Systolic BP  $\geq 120$  mmHg
- If a CT/MR scan has already been performed, then it shows acute intracerebral haemorrhage or ischaemic stroke, or is normal. (If a CT scan has not been performed then it should be performed as soon as possible after treatment)
- For participants who lack capacity to consent for themselves and have no relative/friend available: Waiver of consent for treatment to ensure GTN given in 3-5-hour time-window (and thrombolysis not delayed if ischaemic stroke)

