## TRIAL / STUDY TREATMENT AND REGIMEN

Trial treatment is administered as transdermal glyceryl trinitrate 5 mg patches. Sham treatment comprises a Duoderm dressing. Both are covered with a gauze dressing

Participants will be assessed in hospital (see flow chart)

- Before treatment on day 0.
- 1 hour after treatment on day 0.
- 1 hour after treatment on day 1.
- At discharge/death.

Follow up at day 90 will be via a telephone interview (as in ENOS, RIGHT-2). Researchers will not contact the participant or their family directly at day 90; they will first contact the participant's general practitioner (GP) or obtain information through the Medical Research Information Service/NHS Information Centre to check their health status. Permission to contact the GP at day 90 will be sought at the time of consent. In the event that a participant has been unable to be contacted to perform their follow-up at day 90, researchers will send a letter to their GP to request that they (or another healthcare professional if more appropriate), confirm an appropriate mRS value for the participant and the date on which this value was determined. This aims to reduce data loss associated with participants being lost to follow up.

Brain imaging (CT head scan) will be performed at baseline (Day 0):

- As part of routine clinical management prior to or soon after enrolment – all acute stroke patients have a CT head scan performed on admission to hospital for diagnostic purposes, this including a non-contrast CT scan +/- CT angiogram.

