## RADIATION EXPOSURE

### Details of diagnostic or therapeutic ionising radiation

Participants will have 1 or more CT head scans:

- **Clinical:** A routine clinical CT head scan comprising non-contrast CT shortly after presentation to hospital according to the local clinical imaging protocol; this may be performed before or immediately after trial treatment has been initiated. This CT head scan is part of routine clinical care and is independent of the trial. For patients who are randomised into the trial the scan and results will be used as baseline data.
- **Clinical:** Patients may need additional head CT scans performed for clinical reasons (e.g., deterioration or stroke recurrence); scans and reports from these will also be collected for the study.

These approaches were used in the ENOS and RIGHT-2 trials

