### Details of radioactive materials and dose

1 CT Brain – 2 mSv (utilising mean DLP from recent national survey by Public Health England ref. PHE-CRCE-013 (2014) and conversion co-efficient from Shripton et. al. British Journal of Radiology 89 (2016)). This leads to the following maximum protocol dose; 1 CT Head – 2 mSv

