### Clinical Assessment

The scan itself takes about half a minute and does not involve any injections. The scan uses x-rays, which in large amounts can be harmful, but for this extra CT head scan the additional risk to the participant from the scan has been judged to be extremely small.

The objective of the exposure is to assess the extent of the bleeding (haematoma) in the brain to see if it has got worse (larger) or better (smaller) following treatment. An alternative would be MRI brain scan, but this takes longer, and many patients are unsuitable or unable to tolerate it due to claustrophobia.

The procedure for CT and any doses in lay terms are explained in the participant information sheet.

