#### ***24b Secondary endpoints***

1. Hospital admission:
  - Neurological impairment (NIHSS)
  - Systolic and diastolic blood pressure, heart rate.
  - Proportion of participants with systolic blood pressure <185 mmHg.
  - Feeding and dysphagia (dysphagia severity rating scale)
  - Stroke lesion size on brain scan (non-contrast CT or T2 MR).
  - Amount of cerebral arterial patency on brain scan (CT or MR angiography).
2. Hospital utilisation:
  - Open-label blood pressure lowering.
  - Intravenous thrombolysis.
  - Mechanical thrombectomy.
  - Hyperacute stroke unit.
  - Stroke Rehabilitation Unit.
  - Physiotherapy.
  - Occupational therapy.
  - Speech & language therapy.
  - Surgery for IS - Hemicraniectomy.
  - Surgery for ICH.
  - Days in intensive/critical care unit.
3. At day 2:
  - Systolic and diastolic blood pressure, heart rate.

4. At day 2: Biomarkers
  - Blood biomarkers (exact measures to be determined by literature review prior to measurement but examples include S-100, NOx).
  - Genetic markers (exact measures to be determined by literature review prior to measurement but examples include NO synthase polymorphisms).
5. At day 2 (or discharge if sooner):
  - Neurological impairment (NIHSS).
  - Stroke recurrence.
  - Neurological deterioration from baseline (NIHSS  $\geq 4$  points, or  $\geq 2$ -point increase in any domain).
  - Feeding and dysphagia (DSRS).
6. At discharge/death
  - Length of stay in hospital.
  - Patient disposition.
7. At day 90 by telephone (or post):
  - Dependency – modified Rankin Scale (primary clinical endpoint at Day 90).
  - Disability/activities of daily living - Barthel Index (BI).
  - Quality of life - health utility status (HUS, derived from EuroQoL-5D), EQ-Visual Analogue Scale (EQ-VAS).
  - Cognition - telephone-MMSE, telephone interview cognition scale (TICS), animal naming.
  - Mood - Zung depression scale.
  - Patient disposition (died, institution/in hospital, home).

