**Table 4. Clinical Outcomes at Day 2.**

Data are number (%), median [IQR], or mean (standard deviation).

Variable	Statistic	N	All	GTN	Sham	aOR/aMD (95%CI)	Difference (p)
Patients randomised	N	xxx	xxx	xxx	xxx		
Mechanistic Outcomes							
Blood Pressure							
SBP (mmHg)	Mean (SD)	xxx	xxx (xxx)	xxx (xxx)	xxx (xxx)	xxx (xxx, xxx)	MLR
DBP (mmHg)	Mean (SD)	xxx	xxx (xxx)	xxx (xxx)	xxx (xxx)	xxx (xxx, xxx)	MLR
Heart rate (bpm)	Mean (SD)	xxx	xxx (xxx)	xxx (xxx)	xxx (xxx)	xxx (xxx, xxx)	MLR
Clinical Outcomes							
Impairment							
NIHSS (/100)	Mean (SD)	xxx	xxx (xxx)	xxx (xxx)	xxx (xxx)	xxx (xxx, xxx)	MLR
Neurological deterioration NIHSS change from baseline (point increase)							
NIHSS ≥ 4	Mean (SD)	xxx	xxx (xxx)	xxx (xxx)	xxx (xxx)	xxx (xxx, xxx)	MLR
NIHSS ≥ 2	Mean (SD)	xxx	xxx (xxx)	xxx (xxx)	xxx (xxx)	xxx (xxx, xxx)	MLR
Hand weakness						xxx (xxx, xxx)	OLR
...Normal strength	n (%)	xxx	xxx (xxx)	xxx (xxx)	xxx (xxx)		
...Reduced strength	n (%)	xxx	xxx (xxx)	xxx (xxx)	xxx (xxx)		
...Some movement	n (%)	xxx	xxx (xxx)	xxx (xxx)	xxx (xxx)		
...Paralysis	n (%)	xxx	xxx (xxx)	xxx (xxx)	xxx (xxx)		
Feeding ability						xxx (xxx, xxx)	OLR
...Normal diet	n (%)	xxx	xxx (xxx)	xxx (xxx)	xxx (xxx)		
...Soft diet	n (%)	xxx	xxx (xxx)	xxx (xxx)	xxx (xxx)		
...NG feed	n (%)	xxx	xxx (xxx)	xxx (xxx)	xxx (xxx)		
...PEG feed	n (%)	xxx	xxx (xxx)	xxx (xxx)	xxx (xxx)		
...IV/SC fluids	n (%)	xxx	xxx (xxx)	xxx (xxx)	xxx (xxx)		
...Nothing	n (%)	xxx	xxx (xxx)	xxx (xxx)	xxx (xxx)		
Dysphagia, DSRS (/12)	Mean (SD)	xxx	xxx (xxx)	xxx (xxx)	xxx (xxx)	xxx (xxx, xxx)	MLR
Events up to day 2							
Death	n (%)	xxx	xxx (xxx)	xxx (xxx)	xxx (xxx)	xxx (xxx, xxx)	BLR
Symptomatic ICH	n (%)	xxx	xxx (xxx)	xxx (xxx)	xxx (xxx)	xxx (xxx, xxx)	BLR
ICH expansion	n (%)	xxx	xxx (xxx)	xxx (xxx)	xxx (xxx)	xxx (xxx, xxx)	BLR
Symptomatic Recurrent Stroke						xxx (xxx, xxx)	OLR

Variable	Statistic	N	All	GTN	Sham	aOR/aMD (95%CI)	Difference (p)
...IS	n (%)	xxx	xxx (xxx)	xxx (xxx)	xxx (xxx)		
...haemorrhagic	n (%)	xxx	xxx (xxx)	xxx (xxx)	xxx (xxx)		
...unknown type	n (%)	xxx	xxx (xxx)	xxx (xxx)	xxx (xxx)		
...none	n (%)	xxx	xxx (xxx)	xxx (xxx)	xxx (xxx)		
Clinical neuro-deterioration	n (%)	xxx	xxx (xxx)	xxx (xxx)	xxx (xxx)	xxx (xxx, xxx)	BLR
MEB	n (%)	xxx	xxx (xxx)	xxx (xxx)	xxx (xxx)	xxx (xxx, xxx)	BLR
Acute coronary Syndrome (ACS)	n (%)	xxx	xxx (xxx)	xxx (xxx)	xxx (xxx)	xxx (xxx, xxx)	BLR
...STEMI							
...NSTEMI							
...Unstable angina							
...None							

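### SAP Table 4 compares ICH expansion between arms by adjusted logistic regression, but only one routine day-0 CT is scheduled, so expansion is ascertained selectively and is left undefined

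*SAP*

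**What the plan says.** **The analysis.** SAP Table 4 has a row for "ICH expansion" under events up to day 2, shown as n (%) with an adjusted odds ratio from binary logistic regression. SAP 25d adjusts for age, NIHSS, time after stroke, systolic blood pressure and receipt of reperfusion therapy. SAP 18 says that missing data are reported, and SAP 27 that they are not imputed. Neither document defines expansion.

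**The scans.** The protocol's treatment section says "Brain imaging (CT head scan) will be performed at baseline (Day 0"), as part of routine management. The protocol's participant measures table and SAP Table C show one CT, on day 0 either before or after treatment. The inclusion criteria add: "If a CT scan has not been performed then it should be performed as soon as possible after treatment". The radiation section says of the routine scan that "this may be performed before or immediately after trial treatment has been initiated". It adds that further scans may be done for clinical reasons such as deterioration or recurrence, and that these are collected. On dose it says "This leads to the following maximum protocol dose; 1 CT Head", at 2 mSv.

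**The conflicting text.** The Clinical Assessment paragraph of the same section refers to an additional CT and says: "The objective of the exposure is to assess the extent of the bleeding (haematoma) in the brain to see if it has got worse" or better after treatment.

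**Related endpoints.** SAP 24b, like the protocol's secondary endpoints, lists under hospital admission "Stroke lesion size on brain scan (non-contrast CT or T2 MR") and "Amount of cerebral arterial patency on brain scan (CT or MR angiography").

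**The concern.** A between-arm test implies that the outcome was looked for in the same way in everyone at risk. Here nobody is scheduled for the second scan that expansion requires. Whether it is found depends on a clinician's decision to rescan, which is likely to follow deterioration.

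That decision need not be independent of treatment. The protocol says that staff applying the patches know the allocation and that an investigator can unblind by lifting the gauze. It also lists headache as a common effect of the drug, which could plausibly prompt a scan. No passage shows that rescanning would differ by arm, but nothing in the design prevents it.

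The 20 ICH patients are included on safety grounds. A row with few events could be read as reassurance, and a small imbalance as a signal, when neither reading has systematic imaging behind it. The radiation text adds to this risk, because a reader of that paragraph would believe that haematoma change was assessed in the trial.

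**Working it through.** **1. Scans provided for.** The dose sections give 1 CT × 2 mSv = 2 mSv, and the stated total protocol dose is 2 mSv. Two protocol scans would be 2 × 2 = 4 mSv. The dose figure therefore agrees with the treatment section and both schedules (one CT), and disagrees with the Clinical Assessment paragraph.

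**2. What can be observed in an ICH patient.**

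| First CT | Later clinical CT | What is known about expansion |
|---|---|---|
| Before patch | No | Nothing |
| Before patch | Yes | Change across treatment, in a selected patient |
| After patch | No | Nothing |
| After patch | Yes | Change from a post-treatment starting point only |

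**3. Effect of the undefined denominator (illustration; all rates are assumed, none is in the documents).** Let t be the true expansion risk, and pe and pn the chances of a second scan with and without expansion. Take t = 0.30 and pn = 0.30.

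- Unscanned patients treated as not expanded: observed risk = t·pe.
- Unscanned patients treated as missing: observed risk = t·pe / [t·pe + (1 − t)·pn].

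| pe | As not expanded | As missing | Scanned per 10 ICH patients |
|---|---|---|---|
| 0.70 | 0.21 | 0.21/0.42 = 0.50 | 4.2 |
| 0.50 | 0.15 | 0.15/0.36 = 0.42 | 3.6 |
| 0.30 | 0.09 | 0.09/0.30 = 0.30 | 3.0 |

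Against a true 30%, the two handlings give 9 to 21% and 30 to 50%.

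**4. Consequence for the arm comparison.** Among scanned patients the odds of expansion are t·pe / [(1 − t)·pn]. The odds ratio is therefore multiplied by the ratio of pe/pn between arms. If rescanning works identically in both arms, that ratio is 1 and only the arm-specific risks are wrong. If unscanned patients are treated as not expanded, the observed risk ratio is multiplied by the ratio of pe between arms. Either handling thus biases the comparison once the rescanning probabilities that enter it differ by arm.

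**5. Whether the model can be fitted.** It has a treatment term plus five covariates, so at least six coefficients and an intercept. With 20 ICH patients and t = 0.30 there are 20 × 0.30 = 6 true events. At pe = 0.30 to 0.70 the events seen are 6 × 0.30 = 1.8 to 6 × 0.70 = 4.2 in total, or 0.9 to 2.1 per arm. That is fewer events than coefficients. Even with every patient scanned and no adjustment, 10 v 10 has about 19% power for 30% v 10% (assumed rates; normal approximation, two-sided 5%).

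**6. Lesion size and patency.** Both come from the same day-0 scan, which precedes the patch in some patients and follows it in others; angiography is optional. SAP Table 1 has related baseline rows (compatible lesion, hyperdense artery, CT angiography, large vessel occlusion, onset-to-scan time), but none for lesion size, for a graded patency measure or for scan timing relative to the patch.

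**The case against.** The strongest reply is that this row carries little weight. ICH expansion is not among the declared secondary or safety endpoints, the primary endpoint is feasibility, the comparisons are exploratory, and nothing about progression depends on the row. ICH safety is also covered elsewhere: the Data Monitoring Committee follows serious adverse events, neurological deterioration and outcome separately in ischaemic stroke and ICH. All of this stands, and it limits the consequence. It does not supply the missing measurement or make the regression estimable.

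Three stronger readings are tempting, and the documents do not support them.

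- A reader might infer that ICH patients without a second scan are counted as having no expansion, over everyone randomised. No passage says so. The row has its own N column, and the no-imputation rule fits treating them as missing equally well. The fault is that the SAP does not say which.
- A reader might infer that expansion cannot be measured at all. Clinically prompted scans are collected, so it can be seen in some patients. The fault is selective ascertainment.
- A reader might infer that lesion size and patency are invalid endpoints and must be deleted. They are listed under hospital admission, and the protocol says that the routine scan serves as baseline data. They can be described from that scan, but should not be read as treatment effects.

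**Conclusion.** Wrong as written, with moderate confidence. The planned adjusted comparison of ICH expansion has no systematic measurement behind it, no definition, no stated denominator and no rule for ICH patients with one scan. It concerns about 10 ICH patients per arm, of whom only those rescanned for clinical reasons can contribute. The protocol also contradicts itself on whether a scan for haematoma change exists.

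The absence of a scheduled second scan and the conflict between sections rest on the documents alone. The size of any distortion does not: the 30% expansion risk and the rescan probabilities are assumptions, and bias in the arm comparison further requires rescanning to differ by arm, for which there is no evidence either way. That the model is impracticable depends less on these figures, since even complete scanning would give about six events under the assumed risk.

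**What to change.** 1. **SAP Table 4.** Drop the regression for this row. Report by arm, in ICH patients only: the number with ICH, the number with a baseline and a later scan, the reason for the rescan, whether the first scan came before or after the first patch, and the number expanded. Define expansion. Add a note that absence of a scan is not absence of expansion.
2. **Protocol.** Reconcile the Clinical Assessment paragraph with the treatment section, the participant measures table and the other radiation paragraphs. That paragraph says that the CT procedure and doses are explained in the participant information sheet, so check the sheet for the same text. State in the trial report that haematoma growth was not systematically assessed.
3. **SAP 24b.** Treat lesion size and arterial patency as admission-scan descriptors, tabulated by scan timing relative to the first patch, and do not interpret them as treatment effects. They need not be deleted as endpoints.

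No new scan is asked for. The cost is SAP wording, changes to table shells and a protocol text correction through the usual amendment route. The downside is that one exploratory comparative row is given up.

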**Table 5. Blood pressure and heart rate up to Day 2.**

Data are mean (standard deviation).

Variable	Statistic	N	All	GTN	Sham	aMD (95%CI)	Difference (p)
Patients randomised	N	xxx	xxx	xxx	xxx		
Admission							
SBP (mmHg)	Mean (SD)	xxx	xxx (xxx)	xxx (xxx)	xxx (xxx)	xxx (xxx, xxx)	MLR
DBP (mmHg)	Mean (SD)	xxx	xxx (xxx)	xxx (xxx)	xxx (xxx)	xxx (xxx, xxx)	MLR
Heart rate (bpm)	Mean (SD)	xxx	xxx (xxx)	xxx (xxx)	xxx (xxx)	xxx (xxx, xxx)	MLR
Day 0-2hrs post randomisation							
SBP (mmHg)	Mean (SD)	xxx	xxx (xxx)	xxx (xxx)	xxx (xxx)	xxx (xxx, xxx)	MLR
DBP (mmHg)	Mean (SD)	xxx	xxx (xxx)	xxx (xxx)	xxx (xxx)	xxx (xxx, xxx)	MLR
Heart rate (bpm)	Mean (SD)	xxx	xxx (xxx)	xxx (xxx)	xxx (xxx)	xxx (xxx, xxx)	MLR
Day 1							
SBP (mmHg)	Mean (SD)	xxx	xxx (xxx)	xxx (xxx)	xxx (xxx)	xxx (xxx, xxx)	MLR
DBP (mmHg)	Mean (SD)	xxx	xxx (xxx)	xxx (xxx)	xxx (xxx)	xxx (xxx, xxx)	MLR
Heart rate (bpm)	Mean (SD)	xxx	xxx (xxx)	xxx (xxx)	xxx (xxx)	xxx (xxx, xxx)	MLR
Overall Comparison							
SBP (mmHg)						xxx (xxx, xxx)	RM
DBP (mmHg)						xxx (xxx, xxx)	RM
Heart rate (bpm)						xxx (xxx, xxx)	RM

Please note

RM- Comparison by repeated measures with baseline adjustment

**Table 6. Outcomes at Discharge.**

Data are number (%) and mean (standard deviation).

Variable	Statistic	N	All	GTN	Control	aOR/aMD (95%CI)	Difference (p)
Patients randomised	N	xxx	xxx	xxx	xxx		
Disposition Outcomes							
Discharge destination						xxx (xxx, xxx)	OLR
...Home	n (%)	xxx	xxx (xxx)	xxx (xxx)	xxx (xxx)		
...Institution	n (%)	xxx	xxx (xxx)	xxx (xxx)	xxx (xxx)		
...Hospital	n (%)	xxx	xxx (xxx)	xxx (xxx)	xxx (xxx)		
...Died	n (%)	xxx	xxx (xxx)	xxx (xxx)	xxx (xxx)		
...Other	n (%)	xxx	xxx (xxx)	xxx (xxx)	xxx (xxx)		
Length of stay in hospital, days	Mean (SD)	xxx	xxx (xxx)	xxx (xxx)	xxx (xxx)	xxx (xxx, xxx)	MLR
Hospital Interventions							
Acute stroke unit, ASU	n (%)	xxx	xxx (xxx)	xxx (xxx)	xxx (xxx)	xxx (xxx, xxx)	BLR
Length of stay in ASU, days	Mean (SD)	xxx	xxx (xxx)	xxx (xxx)	xxx (xxx)	xxx (xxx, xxx)	MLR
Intensive therapy/high dependency unit (ITU/HDU)	n (%)	xxx	xxx (xxx)	xxx (xxx)	xxx (xxx)	xxx (xxx, xxx)	BLR
Length of stay in ITU/HDU, days	Mean (SD)	xxx	xxx (xxx)	xxx (xxx)	xxx (xxx)	xxx (xxx, xxx)	MLR
Stroke rehabilitation unit (SRU)	n (%)	xxx	xxx (xxx)	xxx (xxx)	xxx (xxx)	xxx (xxx, xxx)	BLR
Length of stay in SRU, days	Mean (SD)	xxx	xxx (xxx)	xxx (xxx)	xxx (xxx)	xxx (xxx, xxx)	MLR
Non-stroke ward	n (%)	xxx	xxx (xxx)	xxx (xxx)	xxx (xxx)	xxx (xxx, xxx)	BLR
Length of stay in non-stroke ward	Mean (SD)	xxx	xxx (xxx)	xxx (xxx)	xxx (xxx)	xxx (xxx, xxx)	MLR
Physiotherapy	n (%)	xxx	xxx (xxx)	xxx (xxx)	xxx (xxx)	xxx (xxx, xxx)	BLR
Occupational therapy	n (%)	xxx	xxx (xxx)	xxx (xxx)	xxx (xxx)	xxx (xxx, xxx)	BLR
Speech and language therapy	n (%)	xxx	xxx (xxx)	xxx (xxx)	xxx (xxx)	xxx (xxx, xxx)	BLR
Dietician	n (%)	xxx	xxx (xxx)	xxx (xxx)	xxx (xxx)	xxx (xxx, xxx)	BLR
Intermittent pneumatic compression stockings	n (%)	xxx	xxx (xxx)	xxx (xxx)	xxx (xxx)	xxx (xxx, xxx)	BLR
Results of carotid ultrasound (stenosis)							

Variable	Statistic	N	All	GTN	Control	aOR/aMD (95%CI)	Difference (p)
Left stenosis	Mean (SD)	xxx	xxx (xxx)	xxx (xxx)	xxx (xxx)	xxx (xxx, xxx)	MLR
Right stenosis	Mean (SD)	xxx	xxx (xxx)	xxx (xxx)	xxx (xxx)	xxx (xxx, xxx)	MLR
Do not resuscitate (DNR)	n (%)	xxx	xxx (xxx)	xxx (xxx)	xxx (xxx)	xxx (xxx, xxx)	BLR
Final Diagnosis of the randomising event							
Stroke diagnosis							OLR
...Ischaemic stroke	n (%)	xxx	xxx (xxx)	xxx (xxx)	xxx (xxx)	xxx (xxx, xxx)	
...PICH	n (%)	xxx	xxx (xxx)	xxx (xxx)	xxx (xxx)	xxx (xxx, xxx)	
...TIA	n (%)	xxx	xxx (xxx)	xxx (xxx)	xxx (xxx)	xxx (xxx, xxx)	
...Subarachnoid haemorrhage	n (%)	xxx	xxx (xxx)	xxx (xxx)	xxx (xxx)	xxx (xxx, xxx)	
...Stroke type, unknown							
Mimic Haemorrhage							
Non-stroke diagnosis							
...Traumatic brain injury	n (%)	xxx	xxx (xxx)	xxx (xxx)	xxx (xxx)	xxx (xxx, xxx)	
...Seizure/fit	n (%)	xxx	xxx (xxx)	xxx (xxx)	xxx (xxx)	xxx (xxx, xxx)	
...Migraine/headache	n (%)	xxx	xxx (xxx)	xxx (xxx)	xxx (xxx)	xxx (xxx, xxx)	
...Tumour	n (%)	xxx	xxx (xxx)	xxx (xxx)	xxx (xxx)	xxx (xxx, xxx)	
...Abscess	n (%)	xxx	xxx (xxx)	xxx (xxx)	xxx (xxx)	xxx (xxx, xxx)	
...Vestibular/labyrinthine	n (%)	xxx	xxx (xxx)	xxx (xxx)	xxx (xxx)	xxx (xxx, xxx)	
...Neuropathy	n (%)	xxx	xxx (xxx)	xxx (xxx)	xxx (xxx)	xxx (xxx, xxx)	
...Dementia	n (%)	xxx	xxx (xxx)	xxx (xxx)	xxx (xxx)	xxx (xxx, xxx)	
...Subdural haemorrhage	n (%)	xxx	xxx (xxx)	xxx (xxx)	xxx (xxx)	xxx (xxx, xxx)	
...Extradural haemorrhage	n (%)	xxx	xxx (xxx)	xxx (xxx)	xxx (xxx)	xxx (xxx, xxx)	
...Encephalitis	n (%)	xxx	xxx (xxx)	xxx (xxx)	xxx (xxx)	xxx (xxx, xxx)	
...Meningitis	n (%)	xxx	xxx (xxx)	xxx (xxx)	xxx (xxx)	xxx (xxx, xxx)	
...Transient global amnesia (TGA)	n (%)	xxx	xxx (xxx)	xxx (xxx)	xxx (xxx)	xxx (xxx, xxx)	
...Syncope/faint	n (%)	xxx	xxx (xxx)	xxx (xxx)	xxx (xxx)	xxx (xxx, xxx)	
...Urinary tract infection (UTI)	n (%)	xxx	xxx (xxx)	xxx (xxx)	xxx (xxx)	xxx (xxx, xxx)	

Variable	Statistic	N	All	GTN	Control	aOR/aMD (95%CI)	Difference (p)
..Respiratory tract infection (RTI)	n (%)	xxx	xxx (xxx)	xxx (xxx)	xxx (xxx)	xxx (xxx, xxx)	
...Hypoglycaemia	n (%)	xxx	xxx (xxx)	xxx (xxx)	xxx (xxx)	xxx (xxx, xxx)	
....Functional	n (%)	xxx	xxx (xxx)	xxx (xxx)	xxx (xxx)	xxx (xxx, xxx)	
...Alcohol related	n (%)	xxx	xxx (xxx)	xxx (xxx)	xxx (xxx)	xxx (xxx, xxx)	
...Drug related	n (%)	xxx	xxx (xxx)	xxx (xxx)	xxx (xxx)	xxx (xxx, xxx)	
...Other non-CNS sepsis	n (%)	xxx	xxx (xxx)	xxx (xxx)	xxx (xxx)	xxx (xxx, xxx)	
...Other diagnosis							

Please Note:

Home = (Home- independent; Warden-aided flat; Residential home, Home- needing care)

Institution = (Carer's home; Respite care; Nursing home)

Hospital=(Rehabilitation hospital; In hospital with readmission; Still in hospital after admission; Transfer to another hospital- ICU/ITU; Transfer to another hospital- repatriation )

Other diagnosis means not listed above.

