#### At discharge/death

- Length of stay in hospital
- Patient disposition.

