**14 Table C.-Timing of outcome assessments**

Assessments	Screen	Day 0 Baseline Pre- treatment	Day 0 Post- treatment	Day 1 During treatment	Day 2 After treatment	Discharge, Death	Day 90 Telephone
Face-to-face							
Clinical assessment	X 				X	X	
Eligibility screening	X						
CT Scan		X 	or X 				
Consent		X		or X	or X		
Randomisation		X					
GTN/Sham patch			X	X			
mRS		X 					
U & E FBC		X 					
Blood pressure		X 	X	X			
NIHSS		X 			X		
DSRS		X			X		
Blood biomarkers		X 			X 		

Hospital utilisation						X 	
Listed events				X 	X 		
SAEs, non-fatal			X	X	X		
SAEs fatal				X	X	X	X 
mRS							X 
Barthel Index							X 
EuroQoL							X 
Cognition (t-MMSE, TICS)							X 
Mood (ZDS)							X 

CT: Computerised tomography

NIHSS: National Institutes of Health stroke scale

MMSE: Mini-Mental State Examination

mRS modified Rankin scale

SAEs: Serious Adverse Events

1. Routine as part of clinical practice

2. Pre-morbid mRS

3. Biomarkers: soluble markers, genetics

4. Open-label blood pressure lowering, intravenous thrombolysis, mechanical thrombectomy, hyperacute stroke unit, Stroke Rehabilitation Unit, physiotherapy, occupational therapy, speech & language therapy, surgery for IS – hemicraniectomy, surgery for ICH, days in intensive/critical care unit.

5. Hypotension, hypertension, headache, infection

6. mRS [0 to 5, death=6], NIHSS [0 to 42, death=43], DSRS [0 to 12, death=13], GCS [3 to 15, death=2], BI [0 to 100, death=-5], EQ-5D [-0.5 to 1.0, death=0], EQ-VAS [0 to 100, death=-1], t-MMSE [0 to 22, death=-1], TICS-m [0 to 39, death=-1] and ZDS [ $\geq 70$ , death=102.5].

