**18 Analysis populations**

All available data will be used, including overall patients presenting in clinic and screening data where available. Missing data will be reported.

1. Intention-to-treat population (ITT): summaries by treatment group will be provided according to the treatment the participant was randomised to.
2. Safety population: All participants who were randomised will be summarised according to the treatment they received irrespective of treatment.

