### **27 Missing data**

Missing data will not be imputed.

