Acute Coronary Syndrome	n (%)	xxx	xxx (xxx)	xxx (xxx)	xxx (xxx)	xxx (xxx, xxx)	BLR
Elective rehabilitation admission	n (%)	xxx	xxx (xxx)	xxx (xxx)	xxx (xxx)	xxx (xxx, xxx)	BLR
Viral Infections	n (%)	xxx	xxx (xxx)	xxx (xxx)	xxx (xxx)	xxx (xxx, xxx)	BLR

BI: Barthel Index, TICS-m: Telephone interview cognitive scale- modified; t-MMSE: telephone Mini-Mental State Examination ; ZDS: Zung depression scale; quality of life (EQ-5D HSUV, EQ-VAS).

Death scores: mRS (6); BI (5); TICS-m (-1); ZDS (102.5); EQ-5D HSUV (0); EQ-VAS (-1)

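### Length of hospital stay is compared as mean days, with no rule for stays that end in death or are still open at follow-up

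*SAP*

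**What the plan says.** The Protocol (Secondary endpoints) and SAP section 24b both list "Length of stay in hospital" under the time point "At discharge/death". Hospital utilisation is a separate group of endpoints.

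SAP Table 6 has a row for "Length of stay in hospital, days". It is summarised as mean (SD), with an adjusted mean difference from multiple linear regression, in a table headed by the number of patients randomised. Discharge destination, directly above, includes a category for those who died. The note to the table places patients still in hospital in the hospital category.

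On the analysis set, SAP section 18 uses all available data, and "summaries by treatment group will be provided according to the treatment the participant was randomised to". No text limits the length-of-stay row to patients discharged alive.

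The SAP does deal with death for its clinical scales. Note 6 to Table C sets a death value for ten of them, beginning "mRS [0 to 5, death=6], NIHSS [0 to 42, death=43], DSRS [0 to 12, death=13", and the footnote to Table 3 repeats six. Length of stay is in neither list. Section 27 says "Missing data will not be imputed", which does not settle how a stay ended by death is counted. Cox regression is assigned only to death (section 25c and Table 3).

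**The concern.** If the table is programmed as it stands, a patient who dies on day 1 contributes a stay of one day, shorter than that of a patient discharged home on day 5. A shorter mean stay can then come from quicker recovery or from earlier death, and the regression cannot tell them apart. A treatment that prevented early deaths could appear to prolong stay, and one that caused them could appear to shorten it. The comparison could then point the opposite way to the mortality result for arithmetical reasons alone. Patients still in hospital raise a related problem, because their stay has no end date and no rule says what to enter.

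**Working it through.** The documents give no expected value, SD or power for length of stay, so there is no planned figure to reproduce. The check is how large the artefact could be.

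**Inputs from the documents**
- Deaths by end of trial, GTN v control (SAP Table B, Protocol Table 2): ENOS-early 8% v 20%; RIGHT-2 23% v 19%. A patient who died in hospital before the end of follow-up is among these deaths, so each percentage is an upper bound for in-hospital death.
- Arm size: 50 ischaemic plus 10 haemorrhagic = 60 (SAP section 9).

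**Assumptions**
- Mean days to in-hospital death, D: 3 to 10.
- Mean stay of survivors, S: 10 to 20, the same in both arms, so that there is no true effect on stay.

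**Formula.** With a proportion p dying in hospital, the mean stay in an arm is pD + (1 − p)S. Subtracting the arms gives

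GTN − sham = (p_GTN − p_sham) × (D − S).

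The first factor is 0.08 − 0.20 = −0.12 at ENOS-early rates and 0.23 − 0.19 = +0.04 at RIGHT-2 rates. Positive results mean a longer stay on GTN.

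| D | S | ENOS-early: −0.12 × (D − S) | RIGHT-2: +0.04 × (D − S) |
|---|---|---|---|
| 10 | 10 | 0 | 0 |
| 3 | 10 | +0.84 | −0.28 |
| 5 | 15 | +1.20 | −0.40 |
| 10 | 20 | +1.20 | −0.40 |
| 3 | 20 | +2.04 | −0.68 |

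Over the assumed ranges the artefact runs from 0 to 2.0 days longer on GTN at ENOS-early rates, and from 0 to 0.7 days shorter at RIGHT-2 rates. If only half the deaths in each arm occur in hospital, the largest values halve to 1.02 and 0.34 days. The artefact is zero when D = S, and its sign reverses when D exceeds S.

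**Against the noise.** In 5,000 simulated trials of 60 per arm (survivor stay lognormal with mean 20 and coefficient of variation 1; time to death exponential with mean 5), the average difference was −0.55 days at RIGHT-2 rates and +1.79 at ENOS-early rates. The formula gives −0.6 and +1.8. The SD of the difference was 3.45 and 3.52 days. An unadjusted t-test gave p < 0.05 in 4.8% and 7.9% of trials, against a nominal 5%. Covariate adjustment as planned may reduce the noise somewhat; that was not quantified.

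**Dependence on the rule.** If each death were instead scored as 90 days, with S = 20, the difference would be 0.04 × 70 = +2.8 days at RIGHT-2 rates and −0.12 × 70 = −8.4 days at ENOS-early rates. With survivors' stays equal, the rule that the SAP leaves out decides the sign.

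**The case against.** The strongest reply is that the plan never says deaths count as short stays. A reader might infer that the SAP defines length of stay as days to discharge or death in everyone. The documents do not support that as a stated rule. The heading names an assessment time and also covers disposition, Table 6 is titled as outcomes at discharge, and each row has its own N. What stands is that the default reading needs no extra rule, whereas any other reading needs one that is not written.

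A reader might also infer that the arm with more deaths will always look better. That holds only if deaths come before the average survivor's discharge; late deaths after long stays work the other way.

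Nor do the documents support a serious consequence. Comparisons of secondary outcomes are exploratory (SAP section 25c), the Protocol plans no formal assessment of efficacy, and progression rests on recruitment, compliance and follow-up (SAP section 25b). Deaths are reported in Tables 3 and 4 and directly above the length-of-stay row in Table 6, so an attentive reader can see a conflict. This is why the priority is minor.

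Finally, it is tempting to extend the criticism to the ward-specific stays in Table 6. Those rows come under hospital interventions and describe resource use, for which days occupied until death is a legitimate quantity. The point does not carry over to them.

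A competing-risk analysis does answer a different question from mean days. It is the question that suits an outcome recorded at discharge or death, and it removes the ambiguity about what a short stay means.

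**Conclusion.** The point holds as a minor one. For overall length of stay the SAP sets a comparison of means and no rule for in-hospital deaths or unfinished stays. By default an early death enters as a short completed stay. The artefact is 0 to 2.0 days longer on GTN at ENOS-early death rates and 0 to 0.7 days shorter at RIGHT-2 rates. These sizes rest on assumed times to death and survivor stays, on equal survivor stays, and on end-of-trial deaths standing in for in-hospital deaths. In the simulation the SD of the difference at 60 per arm was about 3.5 days, so the artefact would seldom be visible here, and the feasibility conclusion does not depend on it. It is still worth correcting because the trial is meant to inform a definitive one, and a larger sample would shrink the noise but not the bias.

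**What to change.** For the overall length-of-stay row in Table 6, replace the linear regression on mean days with time from randomisation to discharge alive, treating in-hospital death as a competing event:

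- Show the cumulative incidence of discharge alive by arm.
- Fit a (sub)hazard model with the section 25d covariates, in which in-hospital deaths stay undischarged to day 90.
- Censor patients still in hospital at day 90.
- Give median [IQR] stay among those discharged alive as description only, with no test, because survivors are not a randomised comparison.
- State whether a transfer to another hospital, which the Table 6 note groups under hospital, ends the stay.

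Ward-specific stays may remain as descriptive resource use.

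The cost is SAP wording and a few lines of SAS. Table D already has a time-to-event column, and the trial has a death/discharge form; confirm that it records both dates. The downside is that the effect measure is a (sub)hazard ratio, which is less immediate than a difference in days. The rule should be set before database lock and release of the randomisation codes, because choosing it after seeing deaths by arm would be data-driven.
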